To form a reasonable basis of safety for enrolling the expansion cohort of patients, this study will incorporate two safety lead-ins using the first 6 patients and the first 15 patients (50% of the expected total number of patients) to assess the feasibility, safety and tolerability of combining TTFields therapy with concurrent chemoradiation (concurrent enrollment allowed). The safety cohorts will receive TTFields therapy in addition to standard of care. Variations in daily patient positioning will be recorded. Any treatment related adverse effects will be measured, assessed, and graded during the dose-limiting toxicities (DLT) period, from the beginning of therapy until 8 weeks after completion of radiation therapy to capture any potential delayed toxicity following combination (Trimodal) therapy with radiation, temozolomide, and TTFields therapy. DLT include any severe or life-threatening treatment-related adverse effects that preclude further administration of the study treatments, such as radiation, temozolomide, or continuation of TTFields therapy. The DLT assessment period will be limited to the time from start of TTFields through 8 weeks after RT's completion.

The first lead-in cohort will include the first 6 patients to finish the DLT period and be assessed by investigators. If a DLT occurs in 2 or more of the 6 patients, then the study will not move forward and may re-consider the goal dose of TTFields therapy in the main cohort to be reduced by 50% (one out of every two weeks off) and only increased to the standard usage of

continuous treatment 4 weeks after completion of radiation therapy. If a DLT occurs in less than two patients, the study will proceed with the second safety lead-in.

The second lead-in cohort will include the first 15 patients (6 from the first lead-in and 9 additional) to finish the DLT period and be assessed by the Data Safety Monitoring Committee (DSMC). If a DLT occurs in 5 or more of the 15 patients in the second safety cohort, then the study will not move forward with the expansion cohort and may re-consider the goal dose of TTFields therapy in the main cohort to be reduced by 50% (one out of every two weeks off) and only increased to the standard usage of continuous treatment 4 weeks after completion of radiation therapy. If a DLT occurs in less than five patients, the study will proceed with the final expansion cohort.

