After screening and enrollment, the expanded cohort of subjects will be treated with radiation, temozolomide, and TTField therapy for 6 weeks akin to the safety lead-ins. The primary endpoint of treatment related adverse event (TRAE) rate and severity will be recorded and graded based on the NCI Common Terminology Criteria for Adverse Events (CTCAE) version 5.0 and DLT as defined in this protocol. The CTCAE v5.0 criteria can be found at:

https://ctep.cancer.gov/protocoldevelopment/electronic_applications/docs/CTCAE_v5_Quick_Reference_5x7.pdf Building on the already published long term safety data of combining TTField therapy with adjuvant TMZ after radiation therapy, this phase I study aims to assess the safety and tolerability of the device when used with concurrent radiation and TMZ at the initial postoperative or postbiopsy setting. Thus, the toxicity window for the primary endpoints of this study will start when subjects begin combined trimodal therapy (TTFields, RT, and TMZ) and end 8 weeks after completion of the trimodal therapy. After this time, TRAEs and DLTs are not monitored as part of the study endpoints because long term safety of adjuvant TTFields along with TMZ after radiation has been established in the preceding EF-14 trial. After completion of the DLT window, we will analyze and report on the safety and tolerability of combining TTField therapy with radiation and temozolomide prior to adjuvant therapy. We will report on those findings as well as preliminary survival trends that were observed after final completion of the study.

During the initial trimodal therapy phase, all subjects will receive weekly skin exams along with repeat neurologic exams at Day 22 and Day 43 while chemoradiation is underway. After completion of initial chemoradiation, they will have a 4-week hiatus from TMZ chemotherapy but will continue TTField therapy. After the hiatus, an MRI will be performed and TMZ will then be resumed for a minimum of 6 cycles of adjuvant therapy (along with continued TTField therapy for up to 2 years as tolerated) with appropriate laboratory monitoring per the standard of care.

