Two weeks after trimodal therapy, patients will receive a skin exam, scalp assessment and neurologic exam at Day 64 and will also be monitored at 4 weeks (Day 1 of Cycle 1 of adjuvant TMZ) and 8 weeks (Day 1 of Cycle 2 of adjuvant TMZ) after trimodal therapy to assess for post treatment toxicity that may be delayed. After conclusion of the DLT window, the treatment of

patients will be carried out per the standard of care in addition to continued TTFields therapy, as outlined in the clinical trial-related procedures section. The trial will then follow the clinical outcomes including duration of TTF use, completion of 6 cycles of temozolomide, and progression free survival at 6 months, and median overall survival and overall survival at 2 years.

Primary Study Endpoints

- Rate of treatment-related adverse events (TRAЕ)
- Rate of treatment-related severe adverse events (TRSAЕ)
- Rate of Dose-limiting toxicity (DLT)

Given that the primary objective of this study is to determine the safety and tolerability of adding TTField therapy to combined chemoradiation, our primary endpoints are related to safety as follows: Identify the rate of treatment-related adverse events as well as the rate of any severe adverse events during the combined treatment period and up to 8 weeks afterwards. For the same time frame, we will also document and assess the rate of dose-limiting toxicities. Safety of combined adjuvant treatment with TTFields and TMZ chemotherapy outside of the initial radiation is not a primary objective and will not be formally assessed in this study. The above endpoints will be assessed initially in the interim safety analyses involving the safety lead-in cohorts and then also in the main expanded cohort for the final analysis. See statistical methods for further details of the planned analysis. For any skin toxicity grade II or greater, we will also investigate and document, if apparent, whether this was related to the adhesive vs the ceramic disc component of the device.

Secondary Study Endpoints

- PFS6
- Overall survival (median OS and rate of OS at 2 years)
- Objective response by modified RANO criteria
- Median duration of TTFields use and rate of TTF compliance

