Secondary endpoints of this study will provide a preliminary assessment of clinical outcomes by estimating the PFS6 of TTField therapy plus radiation and TMZ chemotherapy followed by adjuvant TMZ for at least 6 cycles and continuous TTField therapy for up to 24 months. Since use of TTField therapy has been deemed safe and is FDA approved in the post-radiation adjuvant therapy setting, treatment will be pursued using standard of care, as outlined in the treatment modalities section. Median OS and rate of OS at 2 years will be analyzed for all subjects that start the TTField therapy along with radiation and chemotherapy. Objective response to therapy will also be assessed by modified RANO criteria (see appendix). The rate of TTFields compliance will be the percentage of patients who used TTFields at least 75% of the minimum recommended usage of 18 hours a day on average, as assessed monthly. Given the limitations of this small phase I study, these secondary endpoints will not be powered for statistical significance but will provide basic trends as a foundation for further study of efficacy

in future phase II/III trials. The above endpoints will be assessed for all patients in the final analysis.

Subject Selection and Withdrawal

The study will enroll subjects with newly-diagnosed glioblastoma (GBM), following surgical resection of the tumor. After informed consent is obtained, subjects will be screened for eligibility based on the outlined inclusion and exclusion criteria. Prospective participants must have had a contrast-enhanced brain MRI post-tumor resection procedure. If the subject had a biopsy alone without resection, a cranial CT may be used instead of a MRI, provided they had a preoperative MRI scan within 14 days of biopsy. Screening can occur after this post-operative imaging is completed.

If a subject stops study treatment on or before Day 1 of Cycle 2 of the Adjuvant TMZ Therapy Phase, they may continue in the trial for observational purposes, if willing, in order to perform the intention-to-treat analysis.

Eligibility Criteria

Patients with the following characteristics will be eligible in the clinical trial:

Inclusion Criteria:

1. GBM or Gliosarcoma by histology

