7. SUBJECT ASSESSMENTS FOR SAFETY AND EFFICACY

The study procedure calendar for this study is provided in **Appendix 3**.

a) Evaluation of Safety and Tolerability**Dose Limiting Toxicity**

Dose limiting toxicities (DLTs) are defined as any severe or life-threatening treatment-related toxicity that precludes the use of a specified dose of any of the study treatments (TTFields, temozolomide, radiation) including continued use of Optune TTFields device at the standard treatment levels and schedule set out by prior studies. This study will prioritize preserving the standard of care for glioblastoma using approved dosing and radiation of temozolomide and radiation.

Toxicities will be graded according to the CTCAE (Version 5.0) scale. If multiple toxicities are seen, the presence of DLT should be based on the most severe toxicity experienced. Dose-limiting toxicities will be defined as any of the following events which occur during the experimental trimodal therapy with TTFields is added concurrently to radiation and temozolomide therapy or during the 8 weeks after RT is completed, and are considered by the investigator to be attributable to TTFields or the combination of TTFields with radiation and/or temozolomide:

- Any Grade > 3 thrombocytopenia, and Grade 4 anemia and neutropenia.
- Any nonhematologic Grade > 3 toxicity (including nausea, vomiting, or diarrhea), excluding alopecia.

- Any Grade 3-4 radiation-induced skin changes that persist for greater than 7 days and does not improve with management recommendations as outlined in toxicity management.
- Any adverse effect deemed by the investigator, patient's primary neuro-oncologist, or radiation oncologist to be life threatening in nature.

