8. STATISTICAL CONSIDERATIONS

Interim analyses of the first and second safety lead-in cohorts will be performed using data collected from the beginning of the study to eight weeks following trimodal therapy for each patient. Patient characteristics will be summarized using means, standard deviations, medians, interquartile ranges, counts, or percentages, as appropriate. Primary endpoints will be summarized using counts and percentages of patients who experienced a treatment-related adverse event, treatment-related serious adverse event, or DLT for safety and stopping rules.

In the second interim analysis, the percentage of patients with inconclusive MGMT methylation status will also be summarized. Patients with inconclusive MGMT methylation status will be removed from the final study analysis, so we will use this percentage to assess the number of additional patients that need to be recruited to meet our sample size requirement of 30 patients. For example, if 2 out of 15 patients have an inconclusive MGMT methylation status at this stage, we will recruit 4 additional patients to meet the sample size requirement.

Using the intention-to-treat approach, the final analyses will be performed on all patients having received at least one day of use from the study device. Patients with an inconclusive MGMT methylation status will be excluded. Patient characteristics will be summarized using

means, standard deviations, medians, interquartile ranges, counts, or percentages, as appropriate.

Primary endpoints will be summarized using counts and percentages of patients who experienced a treatment-related adverse event, treatment-related serious adverse event, or DLT will be reported overall and by event type following trimodal treatment and 8 weeks thereafter to capture any later appearing toxicities. A subgroup evaluation by MGMT methylation status (methylated vs unmethylated) will also be performed.

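### The start of the toxicity window is worded in two ways, so DLTs and TRAEs in the TTFields-only lead-in may or may not count; the OS population has a smaller version of the same problem

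*Combined protocol and SAP*

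**What the plan says.** **Toxicity window**

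- Section 6, Safety Lead-ins: "The DLT assessment period will be limited to the time from start of TTFields through 8 weeks after" completion of RT. The same paragraph has treatment-related effects assessed "from the beginning of therapy until 8 weeks after completion of radiation therapy", and TTFields is the first treatment given.
- Section 6, two paragraphs after the lead-in rules: "the toxicity window for the primary endpoints of this study will start when subjects begin combined trimodal therapy (TTFields, RT, and TMZ"). Section 6, Primary Study Endpoints, lists DLT among these endpoints and describes the period for adverse events as "during the combined treatment period and up to 8 weeks afterwards".
- Section 7a, Dose Limiting Toxicity, limits DLTs to events "which occur during the experimental trimodal therapy with TTFields is added concurrently to radiation and temozolomide therapy" or in the 8 weeks after RT.
- Section 8 takes the interim data from the beginning of the study to eight weeks after trimodal therapy.

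**Order of treatments** (Section 6, Treatment Period): TTFields starts on Day 1 to Day 8 and up to 14 days before RT/TMZ. RT starts by Day 15. TMZ may follow RT by up to 7 days, so by Day 22. The synopsis plans TTFields about 1 week before RT.

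**Survival set**

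- Section 6, Secondary Study Endpoints: "Median OS and rate of OS at 2 years will be analyzed for all subjects that start the TTField therapy along with radiation and chemotherapy". The last sentence of that subsection says the endpoints are assessed for all patients in the final analysis.
- Section 8: "the final analyses will be performed on all patients having received at least one day of use from the study device", followed by an exclusion of patients with inconclusive MGMT status.
- Section 6, on later adjuvant cycles and on long-term follow-up, uses subjects treated for at least one day.

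**The concern.** A device-only interval is part of the design. Skin toxicity is the expected toxicity, and the Day 8 visit, at which RT is started, already calls for a graded and attributed skin examination. Device-only events will therefore be recorded, but the text does not settle whether they count as DLT or TRAE.

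The safety set is everyone with at least one day of TTFields (Section 7, Evaluation of Safety; Section 8). If the window opened only once all three treatments had begun, a patient with a device-only event would stay in the denominator while the event left the numerator. The reported rate could then only fall. The stopping thresholds are small counts in an open-label trial, and with two usable definitions the choice could be made after events are known.

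For survival, a set limited to patients who reach chemoradiation conditions the result on having got through the lead-in.

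**Working it through.** **The plan's own figure.** Section 8 gives 2% to 21% for severe skin irritation with n = 30. The Wilson interval for 2/30 (5% of 30 = 1.5, rounded up to 2) reproduces it:

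- centre = (p + z²/2n)/(1 + z²/n) = (0.0667 + 0.0640)/1.1281 = 0.1159
- half-width = [z/(1 + z²/n)] × √(p(1−p)/n + z²/4n²) = 1.7375 × 0.0560 = 0.0974
- interval = 1.85% to 21.3%

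This figure is not in dispute and does not depend on the window. The documents give no operating characteristics for the stopping rules.

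**Gap between the two possible starts**

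- To RT: Day 15 − Day 1 = 14 days.
- To all three treatments: Day 22 − Day 1 = 21 days.
- The nominal window, Day 1 to Day 106, is 105 days. The gap is 14/105 = 13% or 21/105 = 20% of it. The planned lead of about 1 week is 7/105 = 7%.

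**Effect of one event.** One device-only DLT left uncounted turns 2/6 (stop) into 1/6 (proceed), or 5/15 (stop) into 4/15 (proceed).

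**Stopping probabilities (illustration).** The true DLT rate p and the share s of DLT patients whose only DLT falls in the device-only period are both assumed. The counted rate is q = p(1 − s).

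Stop at 6: P(X ≥ 2) = 1 − (1−q)⁶ − 6q(1−q)⁵.

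- q = 0.20: 1 − 0.2621 − 0.3932 = 34.5%
- q = 0.15 (p = 20%, s = 25%): 1 − 0.3771 − 0.3993 = 22.4%

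The last column is the chance of stopping at either look: at least 2 of 6, or otherwise at least 5 of 15 (exact binomial).

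| True rate p | Share s | Counted rate q | Stop at 6 | Stop at either look |
|---|---|---|---|---|
| 10% | 0% | 10% | 11.4% | 11.8% |
| 10% | 30% | 7% | 6.1% | 6.2% |
| 20% | 0% | 20% | 34.5% | 38.3% |
| 20% | 10% | 18% | 29.6% | 32.4% |
| 20% | 30% | 14% | 20.0% | 21.3% |
| 33% | 0% | 33% | 64.2% | 74.6% |
| 33% | 30% | 23.1% | 42.0% | 47.7% |

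**Survival set.** Assume 12 of 30 alive at 2 years (40.0%).

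- One non-survivor dropped: 12/29 = 41.4%, or +1.4 points.
- Three non-survivors dropped: 12/27 = 44.4%, or +4.4 points.
- One survivor dropped: 11/29 = 37.9%, or −2.1 points.

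**The case against.** The best defence is that the trimodal phase is a named phase that begins before RT. Section 6 marks its Day 1 by the clinic visit, makes TTFields the first step in starting trimodal therapy, and has RT and TMZ begin on Day 8 of that phase. TTFields duration is counted back to trimodal Day 1, and the Appendix 3 calendar places Day 1 under trimodal therapy. On that usage, the three treatments in parentheses name the parts of the phase, and the window opens with TTFields. This reading stands as possible. It is not the only one, because the sentence speaks of combined therapy and lists all three treatments, and Section 7a speaks of concurrent use.

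A reader might infer that the 2/6 and 5/15 rules are themselves run on the narrower window. The documents do not support that. Both rules sit beside the explicit TTFields start, Section 8 takes interim data from the beginning of the study, and Section 7a includes toxicity attributable to TTFields alone. The exposure remains because DLT is also a primary endpoint under the other wording, and Section 7a, where DLT is defined, uses the concurrent wording.

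A reader might also infer that many DLTs fall in the lead-in. Nothing in the documents shows this. The skin criterion in Section 7a concerns radiation-induced changes, which cannot precede RT, and the Optune-specific DLT depends on failure to resume over a month, which would usually be settled after RT has begun.

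On survival, the last sentence of Secondary Study Endpoints and the one-day rule elsewhere already point to the wider set. That answers most of this part, but the OS sentence still says something else.

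**Conclusion.** The point holds as an ambiguity in the definition of the primary endpoints that should be closed. It is not a demonstrated loss of data. The starts can differ by up to 14 days (RT) or 21 days (TMZ), with about 1 week planned before RT, and no text says which wording governs. A single device-only DLT is enough to change either interim decision. The fall from 34.5% to 22.4% rests on an assumed 20% DLT rate and an assumed one quarter of DLTs in the device-only period. It shows sensitivity and is not a forecast.

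Three stronger readings are not supported:

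- Early drop-outs are not lost from the safety analysis. They remain in its denominator, and only their device-only events are in doubt. Loss of the patients themselves could arise only for OS.
- Each dropped patient does not move a survival rate by 1/30, about 3 points. The denominator changes too, and at 12/30 the shift is +1.4 points for a non-survivor.
- The Section 8 final set is not everyone with a day of device use, because it also removes patients with inconclusive MGMT status.

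The survival part is secondary: OS is an unpowered secondary endpoint here, and most of the text already agrees.

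**What to change.** 1. Use one window for TRAE, TRSAE and DLT: first TTFields use through 8 weeks after completion of RT. This is the start that Safety Lead-ins already gives. Put it in the toxicity-window paragraph and Primary Study Endpoints of Section 6, in Section 7a and in Section 8, and apply it at both interim looks.
2. State when the window ends for a patient who uses the device but never starts RT. An end tied to RT is undefined for that patient.
3. Reconcile the synopsis, which times the interim analyses 4 weeks after the last patient's radiation, with the 8-week window in Safety Lead-ins and Section 8.
4. In Secondary Study Endpoints, define the OS set as all patients with at least one day of device use, and say the same in Section 8. Do not simply point to the Section 8 set, since that would carry its inconclusive-MGMT exclusion into OS.

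The cost is wording. Adverse events are assessed from consent, and progression and death are documented for every subject treated at least one day, so no visit or data item is added. The reported toxicity rate may rise slightly.
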